18	Kota Malang	3	243	Intervention
19	Kota Tangerang Selatan	1	184	Intervention
20	Kota Bekasi	2	158	Comparison
21	Kota Surakarta	2	144	Intervention
22	Kota Semarang	2	129	Comparison
23	Kab. Deli Serdang	1	80	Intervention

Table 7. Allocated intervention districts

No	Kab/Kota	Region	Achieved target of HIV testing per semester (2018-2019)	Group
1	Kab. Deli Serdang	1	80	Intervention
2	Kota Medan	1	575	Intervention
3	Kota Palembang	1	694	Intervention
4	Kab. Tangerang	1	391	Intervention
5	Kota Tangerang Selatan	1	184	Intervention
6	Kota Jakarta Barat	1	544	Intervention
7	Kota Jakarta Pusat	1	473	Intervention
8	Kota Jakarta Timur	1	479	Intervention
9	Kota Bogor	2	374	Intervention
10	Kota Depok	2	287	Intervention
11	Kota Surakarta	2	144	Intervention
12	Kota Surabaya	3	568	Intervention
13	Kota Malang	3	243	Intervention
14	Kota Denpasar	3	982	Intervention
15	Kota Sorong	4	415	Intervention

Table 8. Allocated comparison districts

No	Kab/Kota	Region	Achieved target of HIV testing per semester (2018-2019)	Group
1	Kota Bandar Lampung	1	319	Comparison
2	Kota Jakarta Utara	1	612	Comparison
3	Kota Jakarta Selatan	1	448	Comparison
4	Kota Bekasi	2	158	Comparison
5	Kota Semarang	2	129	Comparison
6	Kota Bandung	2	487	Comparison
7	Kota Makassar	3	866	Comparison
8	Kota Jayapura	4	323	Comparison

5. Recruitment and Sample Size

All FSW in intervention districts who meet study eligibility criteria will be offered community screening (see Section C below for intervention implementation guidelines). FSW in comparison districts will continue to receive the current standard package of interventions.

In to be able to detect a 10 percentage point difference in the rate of HIV testing at health facilities between FSW in intervention vs. comparison districts and have 95% certainty that a difference of that magnitude would not have occurred by chance and 90% certainty of detecting a difference of this magnitude if the difference was real/”the truth,” the following sample of FSW will be needed in intervention and in comparison districts:³

$$n \geq [Z_{1-\alpha} (2P(1-P))^{1/2} + Z_{1-\beta} (P_1(1-P_1) + P_2(1-P_2)^2 / (P_1-P_2)^2)] * deft$$

Where:

$Z_{1-\alpha}$ = the Z score for the level of statistical confidence, or statistical precision, desired (for 95%, $Z = 1.96$)

$Z_{1-\beta}$ = the Z score for the desired statistical power (for 90% one-sided test, $Z = 1.282$)

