P_1 = the expected population proportion in the comparison group of districts (set = 0.5 – this is the worst-case scenario and will produced a sample size that is adequate irrespective of the actual proportion)

P_2 = the expected population proportion in the intervention group of districts (set = 0.6 – assume minimum effect size to be realized of 10 percentages points)

$$P = (P_1 - P_2) / 2$$

$(P_1 - P_2)$ = the magnitude of comparison-group differences (or change over time) to be detected with the specified level of precision and power (assumed to be +/- 10 percentage points)

deft = design effect to compensate for clustering at the district level (1.5 assumed).

The required sample size is thus $n \geq 635$ per experimental group; ≥ 761 after 20% allowance for lost-to-follow up

³ Source: Lwanga SK and Lemeshow S. Sample Size Determination in Health Studies: A Practical Manual. Geneva: World Health Organization.

Interpretation: we would need to recruit 761 FSW who self-test for HIV testing in the intervention districts and 761 FSW for HIV testing at health facilities in comparison districts to be able to detect a 10 percentage point difference in the rate of HIV testing at health facilities (intervention vs. comparison districts) to have 95% certainty that a difference of that magnitude would not have occurred by chance and 90% certainty of detecting a difference of this magnitude if such a difference existed.

In order to assess whether “assisted” or “unassisted” community HIV screening among FSW results in a larger increase in the rate of HIV testing at health facilities, we would need samples of size $n \geq 761$ each of FSW who received assisted and unassisted screening in intervention districts, a total of $n \geq 1,522$ FSW in intervention districts, plus $n \geq 761$ in comparison districts.

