Sample size requirements for the third question measurement pertains to the number of FSW who test positive for HIV at a health facility and are thus eligible to initiate treatment. This will depend upon (1) the number of FSW presenting at health facilities for testing and (2) the positivity rate among those tested. Sample sizes should thus be calculated accordingly. If we assume a testing positivity rate of 3%, it is apparent that the expected number of FSWs who would be eligible for treatment will be small and we will lack sufficient statistical power to make meaningful comparisons with comparison districts. For this reason, it is recommended that the impact of community screening among FSW be measured using SIHA data for FSW in both intervention and comparison districts. This estimate of impact derived in this way will be confounded if it were to be the case that interventions other than HIV self-testing were to be better implemented in intervention vs. comparison districts. It might be possible to minimize this potential bias by including measures of intervention implementation performance in the intervention and comparison districts in multivariable analyses. Thus, a large enough sample size is required to ensure sufficient power to determine the difference in the intervention and control districts.

C. THE INTERVENTION

1. General Description of The Intervention

FSW who meet the eligibility criteria will be offered for HIV blood test first. Participants who wish to take the test will then managed according to the current guideline for standard of care. Participants who disagree to take HIV blood test will then be offered screening test with Ora-Quick®. There will be with two options for community HIV screening by Peer Leaders: (1) in a convenient community setting assisted by PL/PE (assisted screening) or (2) in a setting of their own choosing without assistance from PL/PE (unassisted screening). FSW will also be able to access a community-based screening test by following online link from messages spread through WhatsApp number without having to come into contact with outreach workers. The saliva-based Ora-Quick® test kit will be used for community screening.

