In the event that participants' data are collected by paper, a procedure to upload the data into the established online system will be developed. Each data manager in the IUs needs to conduct the procedure regularly. This is to ensure that all data are being captured thoroughly.

F. DATA ANALYSES

The data analyses to be undertaken will be directed to addressing the research questions laid out at the beginning of the protocol and statistical tests appropriate to each specific analysis will be performed to inform the interpretation of results. The specific steps in the data analysis will be as follows:

1. Compare the characteristics of FSWs who receive self-testing and blood testing.

2. Compare the characteristics of FSWs who receive assisted and unassisted self-testing.
3. Compare proportion of FSWs taking confirmatory test out of those who receive the test in the assisted and unassisted self-testing.
4. Compare the proportion of FSWs who receive HIV test out of those who got offered for the test (including self-testing) in the intervention group with proportion of FSWs who receive HIV test in the control group.
5. Compare the proportion of FSWs taking confirmatory test (including self-testing) out of those receive the test in intervention groups and control group.
6. Compare the proportion of HIV positive in the assisted, unassisted (intervention) and HIV positive in the control group.
7. Compare the proportion of ART initiation in the assisted, unassisted (intervention) and the control group.
8. Calculate the cascade of HIV testing and treatment.
9. Compare stigma scores and FSWs who went to a health facility for HIV testing between assisted, unassisted group.
10. Compare the HIV and STI risk behaviors between assisted and unassisted group.

G. CONTINGENCY STUDY DESIGN

Should the OraQuick® test kits not become available in sufficient time to conduct a full-scale cRCT, a smaller-scale study will instead be undertaken. The purpose of the smaller study is the same as the cRCT described above, and the same protocol described above will be implemented. But the comparison is achieved targets between before and after intervention – there will be no comparison districts. The study will be undertaken in three (3) districts. The three districts will be selected from different parts of Indonesia, and they are: Kota Bandung (west part of Indonesia), Kota Denpasar (central part of Indonesia), and Kota Makassar (center-east part of Indonesia).

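### B.5 powers a difference in facility testing between groups of districts, but counts the intervention sample in women who self-test, who on the outreach route have already declined a facility test

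*Combined protocol and SAP*

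**What the plan says.** B.5 (Recruitment and Sample Size) powers a 10-point "difference in the rate of HIV testing at health facilities between FSW in intervention vs. comparison districts". P1 is "the expected population proportion in the comparison group of districts (set = 0.5", described as a worst case. P2 is "the expected population proportion in the intervention group of districts (set = 0.6". Both are therefore rates for groups of districts. With a design effect of 1.5, the stated requirement is 635 per group, or 761 after a 20% allowance for loss.

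The Interpretation changes the unit on the intervention side: "we would need to recruit 761 FSW who self-test for HIV testing in the intervention districts". The comparison side is 761 women for facility testing. For the assisted-unassisted question, B.5 asks for 761 per method (1,522 self-testers) plus 761 comparison women.

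C.1 gives the order of offers: "Participants who disagree to take HIV blood test will then be offered screening test with Ora-Quick". B.1, C.2(a)-(b) and Annex 2 item 7 follow the same order. Two statements do not fit it neatly. B.5 opens by saying that every eligible woman in intervention districts will be offered community screening, and C.1 adds an online route with no outreach contact.

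Section F item 4 reads "Compare the proportion of FSWs who receive HIV test out of those who got offered for the test", and goes on to include self-tests in the intervention group.

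**The concern.** The sample size formula needs the same kind of woman in both arms: one drawn from the population whose facility-testing rate is P1 or P2. A woman who self-tests on the outreach route has been selected by refusing the very outcome that is measured. Recruiting 761 such women does not show how many women stand in the denominator of the district contrast. Setting them directly against comparison women compares a selected subgroup with an unselected group, which randomisation of districts does not protect.

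At stake is Objective 2, whether community screening raises facility testing. A real benefit among decliners could be missed, or even reversed in sign, while the report still cites 90% power.

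**Working it through.** **Inputs.** From B.5: P1 = 0.5, P2 = 0.6, design effect 1.5, Z = 1.96 and 1.282, 635 and 761 women, 20% loss. From C.1 and C.2: a kit follows a declined facility test. Assumptions of this review: u, the share of decliners who screen; c, the share of screened women who then test at a facility; and no facility testing among decliners without a kit.

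**1. The plan's own figure.** Take P as the mean of P1 and P2, 0.55 (the printed P is half their difference, which does not give 635).

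- Z = 1.645: (1.645 × √(2 × 0.55 × 0.45) + 1.282 × √(0.25 + 0.24))² / 0.10² = 422.2, so 423. Then 423 × 1.5 = 634.5 (635), and × 1.2 = 761.4 (761). This reproduces B.5.
- The written Z = 1.96: 518.2, so 519; × 1.5 = 778.5. This does not.

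The stated size therefore rests on a one-sided 5% level. Both levels are shown below.

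**2. If the 10 points is district-wide.** Women who accept the facility test get no kit, so

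P2 = P1 + (1 − P1) × u × c.

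At P1 = 0.5, a 10-point gain needs u × c = 0.10 / 0.5 = 0.20, that is, one decliner in five. The required c is 20% at u = 1, 26% at u = 0.76 and 40% at u = 0.5. The 0.76 is the Zimbabwe acceptability figure in A.4, used only as an illustration; 0.5 is an assumption.

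The unit matters even when the target is met. With u = 1 and c = 0.20 the intervention districts reach 0.5 + 0.5 × 0.20 = 0.60, as planned. Facility testing among the self-testers alone is 20%. Set against comparison women at 50%, a true gain of 10 points would look like a deficit of 30.

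**3. If the 10 points is the gain among self-testers only.** The district-wide gain is 0.10 × 0.5 × u: 5.0 points at u = 1 and 3.8 at u = 0.76. Behind 761 self-testers stand 761 / (0.5 × u) women offered a test: 1,522 or 2,003. Less 20%, that is 1,218 or 1,602, against 761 × 0.8 = 609 comparison women.

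Power = Φ((d − Z × SE0) / SE1), with SE0 pooled, SE1 unpooled and each n divided by 1.5. For 1,218 against 609 (812 and 406 after the design effect) and d = 0.05, both SEs are 0.0303. Z = 1.96 gives Φ(−0.31) = 38%; Z = 1.645 gives Φ(0.00) = 50%.

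| Gain | Women analysed | Z = 1.96 | Z = 1.645 |
|---|---|---|---|
| 10 points | 1,218 v 609 | 91% | 95% |
| 5 points (u = 1) | 1,218 v 609 | 38% | 50% |
| 3.8 points (u = 0.76) | 1,602 v 609 | 26% | 37% |

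**4. How far this depends on P1.** Table 4 sums to 9,775 tests per semester and Table 5 to 52,972 women reached per year: a crude 18%, or 37% if the tests are doubled. Neither is a rate among women untested for six months, so they serve only as a range. With u = 1 and a 10-point gain among self-testers, intervention n = 761 / (1 − P1) × 0.8:

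| P1 | Most who can get a kit | District gain | Women analysed | Z = 1.96 | Z = 1.645 |
|---|---|---|---|---|---|
| 0.50 | 50% | 5.0 points | 1,218 v 609 | 38% | 50% |
| 0.37 | 63% | 6.3 points | 966 v 609 | 52% | 65% |
| 0.18 | 82% | 8.2 points | 742 v 609 | 84% | 90% |

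**The case against.** The strongest reply is that P2 is defined for the group of districts, so the 10 points is already district-wide and nothing is diluted. On that definition 635 per group does give 90% power at the one-sided level (83% with Z = 1.96). This stands, and it rules out reading the low power figures as fact. It also means that the self-tester count in the Interpretation is the wrong unit, so B.5 still needs correcting.

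A reader might infer that the trial's power is only 19 to 38%. The documents do not support this. It takes the 10 points as an effect among self-testers, which B.5 nowhere says. The 19% comes from 609 against 609 at 3.8 points; yet if self-testers are at most half of the women offered a test, 761 of them imply at least 1,522 intervention women. It also uses a foreign acceptability figure as Indonesian kit uptake.

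Nor do the documents say that at most half of women can receive a kit. That follows only from the worst-case P1 on the outreach route; lower facility uptake or online ordering raises the share. The plan also pays for confirmatory tests after reactive and non-reactive results (C.5), so linkage of 20% of decliners or more is not implausible.

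Finally, item 4 of section F already uses women offered a test as its denominator. That is correct, but it counts self-tests, so dilution does not apply to it and it does not answer Objective 2. No listed item compares facility testing alone among all women offered.

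**Conclusion.** The point holds as a mismatch of unit. B.5 powers a contrast between groups of districts, and its Interpretation counts a self-selected subgroup on one side. The 90% does not belong to 761 self-testers.

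The firm consequence is the unstated condition: at P1 = 0.5, a 10-point district gain needs about 20% of all decliners to reach a facility after the kit offer, provided they would not otherwise have tested there. The loss of power is a scenario. It applies only if the 10 points was meant as the gain among self-testers, and it rests on P1 = 0.5, the outreach route, the design effect of 1.5 as given and 20% loss. It shrinks as P1 falls and grows as kit uptake falls.

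**What to change.** 1. In the B.5 Interpretation, replace the 761 self-testers with women offered a facility test in each arm, whether or not they later self-test (E.3 row 2). Say whether women who enter online are counted. Keep 761 per method for the assisted-unassisted question only.
2. State P2 = P1 + (1 − P1) × u × c, with u × c = 0.20 for 10 points at P1 = 0.5. Print power for smaller district-wide gains as labelled scenarios, and reconcile Z = 1.96 with the 635.
3. Add to section F, for Objective 2, a comparison of facility testing alone among all women offered in both arms: E.3 rows 2 to 4, plus facility tests after screening, whatever the screening result.
4. Reconcile the B.5 sentence on offering screening to all eligible women with the decline-first order in C.1 and C.2.

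The cost is text, a short power table, a less favourable power figure for modest gains, and one count. E.3 row 9 records later facility tests only after reactive screens, and the reactive-or-non-reactive count is listed only for the unassisted route, so the assisted non-reactive count must be added.

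Whether more women are needed stays open. Table 5 outreach over seven of twelve months comes to about 21,600 contacts in intervention and 9,300 in comparison districts. Those are contacts before eligibility, and a design effect of 1.5 cannot be held fixed as women per district increase.

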
3. Implementation Guidelines: Unassisted Community Screening

Because of differences in the structure of sex work and in the enabling environment in different districts, it will be necessary to develop the details of unassisted community screening on a district-by-district basis. Ideally, the same unassisted community screening intervention would be implemented in the same way in all intervention districts, but if this is not possible due to the factors outlined above, allowing some details to vary across districts is preferable to trying to implement a standard protocol that is expected a priori to fail in some locations.

For unassisted community screening, in which OW don't have face-to-face contact with FSWs, possible mechanisms for distributing Ora-Quick test kits entail:

- a. Trained PE/PL identifying various online networks in which FSWs use to solicit their service.
- b. Trained PE/PL building trust from FSWs to participate in the study.
- c. Trained PE/PL send broadcast message containing brief information of the study, eligibility criteria for participation, step-by-step method to order the kit and have it delivered to their address, short link for description of how to use the kit (flier or short video), and mandatory baseline and post-test survey. Test kit delivery will be done by same-day delivery system (Go-Send/Grab Send) from selected places where the test kit will be stored (Implementing Unit Office or selected health care facilities) to client's address. Trained peer leader/peer educator could also distribute the test kit but not participating in the testing by assisting FSW during the test.

- d. Trained PE/PL carrying out follow-up for FSWs being previously approached for the test. The same trained PE/PL is assigned to be the contact person/hotline for each FSW they approached and agreed to take the test.
- e. FSW send/upload results of the test along with a completed post-test survey. Cash (mobile top-up) incentive will be transferred to FSW who send the test results and post-test survey. Every kit distributed will have unique code and FSW will be asked to fill it in both baseline and post-test survey to ensure one FSW is entitled to only one test kit.

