- How likely is it that the client will get a HIV test at a health facility as a result of the community screening test, on a scale of 1-5
- Comments and suggestions.

3. Routine Recording

Because of limitations in the data recorded and reported by health facilities, the study will rely primarily upon data recorded by IU outreach staff. Modifications will be made to the data recording and reporting systems currently being used to facilitate collection of the data needed for the study in a manner that minimizes additional recording and reporting burden. The nature of the adjustments to be made will be different for "assisted" and "unassisted" community screening.

To capture the data needed for of this study, the following data need to be recorded:

No	Data Recorded	Intervention Group	Control Group
1	Number of FSW contacted via outreach that were at least 6 months since their last HIV test for whom testing at a health facility was recommended	Yes	Yes
2	Numbers of FSW offered for HIV test at health facility	Yes	Yes
3	Numbers agreeing and disagreeing to testing at a health facility	Yes	Yes
4	Of those agreeing to getting tested at a health facility, the numbers that actually went to a health facility and were tested for HIV	Yes	Yes
5	Number of FSW offered for OFT screening	Yes	No
6	Among FSW not agreeing to be tested at a health facility, the numbers that agreed to (1) assisted community HIV screening and (2) unassisted community HIV screening	Yes	No
7	Numbers that were actually screened, assisted and unassisted	Yes	No
8	The number of community screening tests that were reactive	Yes	No
9	Among FSW with reactive community screening tests, the numbers that were subsequently tested at a health facility	Yes	No
10	Number of FSW initiating ART	Yes	Yes

For **unassisted** approach, additional information will be gathered as indicated below:

1. Numbers of FSW who access the link online
2. Numbers of FSW who are deemed eligible
3. Numbers of FSW who fill in baseline survey and agree to participate
4. Numbers of FSW who agree to take HIV test at health facility
5. Numbers of FSW who request the kit being delivered vs picking-up at fixed location
6. Numbers of FSW who upload the test result
7. Numbers of reactive vs non-reactive test result
8. Numbers of FSW who complete the post-test survey

9. Among FSW with community screening tests, the numbers that were subsequently tested at a health facility (reactive OR non-reactive)
10. Number of FSW initiating ART

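### Broadcast-link women enter the intervention arm only once they have responded, with no counterpart in comparison districts, so the any-test uptake comparison (F.4) may be biased upward

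*Combined protocol and SAP*

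**What the plan says.** - **Entry route.** Section C.1 opens an online route in intervention districts: "FSW will also be able to access a community-based screening test by following online link from messages spread through WhatsApp number without having to come" (the sentence ends by removing any need to meet an outreach worker). Section C.3 describes how: "Trained PE/PL send broadcast message containing brief information of the study, eligibility criteria for participation, step-by-step method to order the kit".
- **Counting online.** In the additional unassisted list of section E.3, the first item is "Numbers of FSW who access the link online". Then come eligibility (item 2), "Numbers of FSW who fill in baseline survey and agree to participate" (item 3), agreement to a facility test (item 4), kit request (item 5) and upload (item 6). The number of women who received the message is not listed.
- **Counting through outreach.** The main E.3 table starts both arms at row 1: women contacted by outreach who are at least six months past their last test. This count precedes any decision about testing.
- **Comparison districts.** Section C.4 adds nothing to the standard programme there, so no woman can enter by broadcast.
- **Analysis.** Section F item 4 reads "Compare the proportion of FSWs who receive HIV test out of those who got offered for the test (including self-testing) in the intervention group" and sets this against the control arm "with proportion of FSWs who receive HIV test in the control group". It gives no control denominator and no online definition of an offer. No listed analysis splits women by route.
- **Who receives the link.** Section B.1 gives it to women already met, after they decline a facility test. Section C.1 also gives it to women never met. No listed data item tells the two groups apart.

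**The concern.** An outreach woman is counted because a worker met her, whether or not she wants a test. A broadcast woman is counted because she responded to a message about testing. If both kinds are pooled as women offered a test in one arm, while the other arm has only the first kind, the two proportions are not on a common footing.

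Whenever uptake among online entrants exceeds uptake among outreach women, the intervention proportion rises even if self-screening changes nothing for a woman met by outreach. F.4 is the listed analysis closest to Objective 1 (knowing one's status), so a primary conclusion could partly reflect who was counted. Without a route flag taken at entry, the mixture cannot be separated afterwards.

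**Working it through.** **The plan's own figures.** Section B.5 sets P1 = 0.5, P2 = 0.6, power 90% and a design effect of 1.5. With one-sided 5% (z = 1.645) and the mean proportion 0.55:

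n = [1.645·√(2·0.55·0.45) + 1.282·√(0.25 + 0.24)]² / 0.10² = 422.03, taken as 423.

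423 × 1.5 = 634.5, which matches the stated 635. 634.5 × 1.2 = 761.4, which matches 761. The intervention total is 2 × 761 = 1,522 *screened* women. (The printed z of 1.96 gives 519 × 1.5 = 778.5; that is a separate matter and does not affect this point.)

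**Bias formula.** Suppose there is no true effect and outreach uptake of any test is 0.5 in both arms. The plan uses 0.5 for facility testing, and I borrow it here. Pooled intervention uptake is (1 − s)·0.5 + s·u, so the spurious difference is s(u − 0.5).

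**Online share s.** The documents do not give it. Assume half of the 761 unassisted women come by broadcast: 380.5 online and 1,522 − 380.5 = 1,141.5 screened through outreach. These are women screened, so each must be divided by uptake to recover women offered.

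| Case | Online entrants | Outreach women offered | s | Spurious difference |
|---|---|---|---|---|
| u = 0.9, no outreach woman takes a facility test | 380.5/0.9 = 422.8 | 1,141.5/0.5 = 2,283 | 422.8/2,705.8 = 15.6% | 0.156 × 0.4 = 6.3 points |
| u = 0.9, facility testers equal outreach self-screeners | 422.8 | 2,283/0.5 = 4,566 | 422.8/4,988.8 = 8.5% | 0.085 × 0.4 = 3.4 points |
| u = 0.7, no outreach woman takes a facility test | 380.5/0.7 = 543.6 | 2,283 | 543.6/2,826.6 = 19.2% | 0.192 × 0.2 = 3.8 points |

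The first and third rows are maxima for their inputs, because every outreach woman who accepts a facility test enlarges the outreach denominator.

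**Sensitivity to the online fraction** (u = 0.9, no outreach facility testers):
- A quarter of the 761 online: 190.25/0.9 = 211.4 entrants against 1,331.75/0.5 = 2,663.5, so s = 7.4% and the difference is 2.9 points.
- All 761 online: 845.6 against 761/0.5 = 1,522, so s = 35.7% and the difference is 14.3 points. This is an extreme, since section B.1 also has kits delivered by peer workers.

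**Chance of a false finding.** F.4 has no sample size of its own. As an illustration at the planned effective size (635/1.5 per arm, one-sided 5%), spurious differences of 3, 4 and 6 points would be declared significant with probability 22%, 32% and 54%.

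**Why the definition matters.** In the first case, uptake on link entrants is 1,522/2,705.8 = 56%. If offered meant everyone who received the message, and 20% of recipients opened the link (assumed), the denominator would be 2,283 + 422.8/0.2 = 4,397 and uptake 1,522/4,397 = 35%. The second figure could not be computed from the listed counts.

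**The case against.** - **Women are not counted only once they ask for a kit.** A reader might infer that they are. The documents do not support this: link access, eligibility, baseline and facility-test agreement are all listed before the kit request, so women who open the link and order nothing can be counted. If link openers are the denominator, u may be well below 0.9. What stands is that the earliest count is still of responders, and the plan does not say which count F.4 uses.
- **Pooling is not stated.** F.4 does not say in terms that broadcast women are added to outreach women. But the item includes self-testing and splits nothing by route, so an analyst following it may pool them.
- **Section B.1 describes link users who have already been met and offered a facility test.** For them the concern does not apply. It applies to the women in C.1 who were never met. C.3 offers only possible mechanisms, to be settled district by district, and Figure 1 and the Annex 1 flowchart were not readable in the text available to me.
- **The bias might seem to consume the whole planned effect.** A reader might treat 380.5/1,522 = 25% as the online share and reach 0.25 × 0.4 = 10 points. That does not follow: 1,522 counts women screened, not women offered a test, and the planned 10 points refers to testing at health facilities, for which F.4 sets no equivalent target.
- **Online reach is part of the intervention.** Section A.1 gives hidden, online sex work as a reason for new strategies. This stands: these women should not vanish from the arm contrast, and there is no case for applying the same restriction to F.5 to F.7.

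**Conclusion.** The concern holds for F.4 and Objective 1. The plan permits a responders-only denominator for part of one arm, has no counterpart in the other, and lists no data item to separate them. The any-test difference may be biased upward, provided online uptake exceeds outreach uptake.

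With half of the unassisted women online, outreach uptake of 50% and u = 0.9, the bias is at most about 6 points. It is about 3 points if outreach facility testers equal outreach self-screeners, and at most about 4 points if u = 0.7. All of these inputs are assumptions, and the result moves with the online fraction.

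A reader might extend this to the facility-testing outcome that drives the sample size. The documents do not support a direction there, since women who choose a home kit may be less likely to attend a facility. The comparison using SIHA data recommended in section B.5 does not use this denominator and is unaffected.

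**What to change.** 1. Record route of entry (outreach contact or broadcast link) at first contact.
2. Make the main F.4 between-arm comparison on outreach-contacted eligible women (E.3 row 1) in both arms, including those met by outreach who then use the link.
3. Report broadcast-only women as a separate cascade and in a per-district count of tests, and add a sensitivity analysis that puts them into the intervention arm of F.4.
4. Reconcile sections B.1, C.1, C.3, E.3 (unassisted item 4) and Annex 2 item 7 on whether and where online women receive the facility-test offer. C.1 places that offer first and E.3 counts its acceptance, but the online steps in B.1 and C.3 do not show it, and Annex 2 has peer workers record it during outreach.

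The cost is one data field, analysis wording and, depending on item 4, a change to the web form. The other counts needed are already planned. The downside is that the main F.4 proportion no longer credits online reach; the separate cascade, the district count and the sensitivity analysis show it instead.
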